##### **Secondary Objectives**

The secondary objectives are to evaluate during the follow-up period in infants and children who have been treated with lumicitabine or placebo in Study 64041575RSV2004:

- The frequency of wheezing over time.
- The frequency of wheezing episodes over time.
- The long-term safety of lumicitabine.
- The frequency and type of respiratory infections.
- Medical resource utilization.

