## 3. STUDY DESIGN AND RATIONALE

### 3.1. Overview of Study Design

This is a global multicenter, blinded, LTFU study to evaluate the incidence of the clinical diagnosis of asthma and the frequency of wheezing in infants and children (otherwise healthy or with underlying comorbidities for severe RSV) who have completed their treatment course and their last planned study-related visit in a previous Phase 2 study, 64041575RSV2004, in which they received lumicitabine or placebo for the treatment of RSV infection. Subjects will be followed for at least 2 years following treatment. Participation in this LTFU study is optional for study sites. This LTFU study will be offered to subjects of Study 64041575RSV2004 if their site decides to participate in the LTFU.

No study drug will be administered in this study. Subjects may be enrolled within 3 months after randomization in Study 64041575RSV2004. Assessments will be performed at the time points specified in the [Time and Events Schedule](#). The last visit of Study 64041575RSV2004 (ie, Day 28) may be combined with the entry visit of this LTFU study.

Parents/caregivers will be provided with a wheezing parent/caregiver card and a medication parent/caregiver card, both of which should be completed on a daily basis. These parent/caregiver cards will serve as reminder cards when a study site responsible person interviews the subject’s parent/caregiver in order to complete a standardized paper questionnaire. The questionnaire will be completed by a study site responsible person at each study site visit as noted in the [Time and Events Schedule](#) and during a monthly telephone call (calendar month  $\pm 7$  days) between study site visits (see Section 9.1.3).

An unblinded interim analysis will be performed when all subjects from the first season in Study 64041575RSV2004 who are enrolled in this LTFU study complete the 18 months follow-up assessment of this LTFU study. Sites and the parents/caregivers of subjects will remain blinded. This interim analysis will serve to evaluate the need for an extension of the follow-up period (see Section 11.6).

The planned total study duration for each subject will be 24 months unless the decision is taken to extend the duration of follow-up in this study, based on the interim analysis.

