2.3. Analysis Sets

2.3.1. All Enrolled Analysis Set

The All Enrolled analysis set includes all subjects who were enrolled in this LTFU study. The All Enrolled set will be analyzed as treated.

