Incidence of reportable AEs and SAEs, including AEs related to respiratory illnesses and AEs considered at least possibly related to lumicitabine or placebo by the investigator.	These incidences are defined as the number of AEs overall and by category divided by the 2 year reporting period. Each AE is counted as reported. The unit will be ‘per month/during the first 2 years’. In case the subject did not report on the full 24 months the divisor will be adapted to nearest number of months participating.
Number of respiratory infections per subject during study participation	The total number of respiratory infections of each subject. The unit will be ‘during study participation’. The respiratory infection AE terms (AEDECOD) will be determined based on medical review and reported overall and by Preferred Term.
Medical resource utilization including the number of medical visits, emergency room visits, and hospitalizations, all for respiratory conditions only, based on information reported by the parent/caregiver.	Total number of medical visits, emergency room visits, and hospitalizations, as reported by the parent/caregiver. The number will be given overall and by relationship to respiratory conditions, as based on medical review.

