5.2.2. Analysis Methods

Descriptive statistics will be used to present the percentage of wheezing days and the number of wheezing episodes per Month. Frequency tabulations will be used to summarize the number and type of respiratory infections per subject by previous treatment group.

Listings will be provided showing the reported information on wheezing and respiratory infections together with the derived efficacy parameters above. A summary will be provided for respiratory infections:

- any respiratory infections,
- serious respiratory infections,
- deaths due to respiratory infections,
- respiratory infections by toxicity grade,
- respiratory infections at least possibly related to study medication,
- serious respiratory infections that were at least possibly related to study medication

Listings will be provided for all respiratory infections.

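### Respiratory infections are compared between arms only as undivided per-child totals; add infections per child-year beside the count

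*SAP*

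**What the plan says.** The protocol's secondary objective (section 2.1.1) is "The frequency and type of respiratory infections". The matching endpoint in section 2.1.2 is worded as a number and type, not a rate.

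SAP Table 2 labels the endpoint "Number of respiratory infections per subject during study participation" and defines it as "The total number of respiratory infections of each subject". The infections are picked out of the coded adverse-event terms by medical review and reported overall and by preferred term. No divisor is given. Section 5.2.2 then states: "Frequency tabulations will be used to summarize the number and type of respiratory infections per subject by previous treatment group". None of the infection summaries listed there uses time observed, and none is limited to completers.

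The row directly above, for reportable adverse events, does account for time: "These incidences are defined as the number of AEs overall and by category divided by the 2 year reporting period", and "In case the subject did not report on the full 24 months the divisor will be adapted to nearest number of months participating".

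Follow-up is planned as equal but need not turn out so. Protocol section 3.1 says: "The planned total study duration for each subject will be 24 months unless the decision is taken to extend". Section 10.2 provides for withdrawal through loss to follow-up, withdrawn consent or death, and SAP 4.2 tabulates discontinuations. Early leavers stay in the analysis: "The All Enrolled analysis set includes all subjects who were enrolled in this LTFU study". SAP 2.4 gives the number enrolled as 7.

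**The concern.** A total that accumulates with time in the study measures frequency only if everyone is observed equally long. Here a child seen for 6 months and a child seen for 24 months enter the same table as though they had the same opportunity to report infections. SAP 2.1 leaves missing visits unimputed, and SAP 5.2.1 drops the protocol's two imputation methods, so unobserved months add nothing to a child's total. An arm with an early leaver would show fewer infections for that reason alone.

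The SAP deals with this elsewhere. The primary wheezing percentage is divided by days in study, monthly wheezing summaries are per month, the two-year episode count is confined to children who completed, the adverse-event row adapts its divisor, and medical encounters, although an undivided total in Table 2, are tabulated per month in section 7.2. The infection endpoint has no such provision. The study tests no hypothesis, so these descriptive tables by treatment group are the whole result and a reader should be able to interpret them directly.

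**Working it through.** The documents give no target, rate or event figure for this endpoint, so there is nothing of the plan's own to reproduce. The check shows how the planned summary behaves.

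**Inputs from the documents:** 24 months' planned follow-up (protocol 3.1); 7 children (SAP 2.4); count with no divisor (SAP Table 2).

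**Assumptions, not in the documents:** a constant infection rate, the same for every child, taken as 2, 4 or 6 per year; arm sizes of 5 and 2, or 4 and 3; one child leaving one arm at month m.

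**Step 1, one child.** Expected count = rate × m/12. A completer's expected count = rate × 2. The ratio is m/24, whatever the rate:

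- month 3: 3/24 = 12.5%
- month 6: 6/24 = 25%
- month 12: 12/24 = 50%
- month 18: 18/24 = 75%

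At 4 per year the counts are 1, 2, 4 and 6, against 8 for a completer. Divided by months observed, each gives 0.333 per month. Rates of 2 and 6 per year give 0.167 and 0.500 per month, again whatever the exit month.

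**Step 2, one arm.** With n children and one leaver, the arm's mean count falls by (1 − m/24)/n. The SAP specifies a frequency tabulation, so the mean is used here only to gauge the shift.

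| Arm size n | Exit at month 6: 0.75/n | Exit at month 12: 0.50/n | Exit at month 18: 0.25/n |
|---|---|---|---|
| 5 | 15% | 10% | 5% |
| 4 | 19% | 12.5% | 6% |
| 3 | 25% | 17% | 8% |
| 2 | 37.5% | 25% | 12.5% |

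**Step 3, the pooled rate.** Take an arm of 3 at 4 per year with one exit at month 6. Infections: 8 + 8 + 2 = 18. Child-months: 24 + 24 + 6 = 54. Rate: 18/54 × 12 = 4.0 per child-year, the true value. The mean count is 18/3 = 6, against 8 with full follow-up.

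**Step 4, why pooled.** Suppose instead that the third child left after 1 month with 1 infection. That child's own rate is 12 per year, and the mean of the three rates is (4 + 4 + 12)/3 = 6.7. The pooled rate is (8 + 8 + 1)/(24 + 24 + 1) × 12 = 17/49 × 12 = 4.2. Total events over total time is much less disturbed by a short observation.

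**The case against.** The SAP follows the protocol. The endpoint in protocol 2.1.2 is a number, and section 11.3.2 asks for descriptive statistics and frequency tabulations of it. The protocol also uses frequency loosely: the objective on the frequency of wheezing episodes maps to a number of episodes. The adverse-event endpoint is called an incidence and is divided; the infection endpoint is called a number and is not. This stands, and it is why the count should not be replaced.

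A time-adjusted respiratory figure is already planned in part. The adverse-event row is computed by category, and respiratory illness is one of the categories in SAP 6.1.1. This also stands, but that category is broader than the medically reviewed infection terms and gives no infection rate by preferred term.

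The endpoint's label discloses the open window, disposition is tabulated by arm, and all infections are listed. With 7 children a careful reader could probably reconstruct exposure. That limits the harm, but nothing in the SAP calls for months observed to be shown beside the count.

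A rate has weaknesses of its own. The protocol's introduction describes RSV as seasonal in temperate regions, so a few months of observation depend on which months they were, and the constant rate used above is a simplification. This argues against averaging per-child rates and for treating even the pooled rate as descriptive.

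A reader might infer that early departures have biased this study, or that the count could create or reverse a difference between lumicitabine and placebo. The documents support neither. They report no early departure, do not give the arm split, and specify no test.

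**Conclusion.** The point holds as a gap in the planned presentation. As written, the infection summary by treatment group mixes frequency with length of follow-up, although the objective is frequency and the neighbouring row already adjusts for time. The size depends on facts the documents do not give: at a constant rate, a child leaving at month m contributes m/24 of the full-period count, and one exit at month 6 lowers an arm's mean by 15% to 37.5% for arms of 5 down to 2. The direction between arms is unknown, and if all 7 children completed 24 months the effect is negligible. The protocol-defined count is not itself wrong; it lacks its denominator.

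**What to change.** Keep the per-child count in SAP Table 2 as the endpoint. In SAP 5.2.2 add, by previous treatment group:

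- total respiratory infections;
- total child-months of participation, from the participation time already needed for the adverse-event row;
- pooled infections per child-year (total infections divided by total child-months, times 12), overall and by preferred term, and not a mean of per-child rates.

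In the listing, show months observed beside each child's count. State that the rate is descriptive, imprecise with 7 children and dependent on the seasons observed.

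The cost is a few lines of SAP text and one extra derived display. No new data are needed.

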5.2.2. Analysis Methods

Descriptive statistics will be used to present the percentage of wheezing days and the number of wheezing episodes per Month. Frequency tabulations will be used to summarize the number and type of respiratory infections per subject by previous treatment group.

Listings will be provided showing the reported information on wheezing and respiratory infections together with the derived efficacy parameters above. A summary will be provided for respiratory infections:

- any respiratory infections,
- serious respiratory infections,
- deaths due to respiratory infections,
- respiratory infections by toxicity grade,
- respiratory infections at least possibly related to study medication,
- serious respiratory infections that were at least possibly related to study medication

Listings will be provided for all respiratory infections.

5.3. Exploratory Endpoints

5.3.1. Definition

For the exploratory endpoints the data will be presented using for each subject a row for each month (based on the assignment in the database), and columns presenting the data to each subsequent question of the interview.

The same lay-out will be used to provide summary statistics for endpoints as defined below by treatment group and study Month. The definitions of these endpoints are given in [Table 3](#). Parameters will be assigned to the monthly visits based on the assignment in the database.

Table 3: Calculations and Conversion Formulae (Exploratory Endpoints)

Measurement	Calculation
Subject's daily activities limited by the subject's health per Month	The parent/caregiver reports that they are not working due to the child's health problems. The answer to Questionnaire section E question 1. The result will be either "Yes" or "No" and will be calculated for Screening and each Month as based on the assignment in the database.
Percentage of days per Month the parent/caregiver missed from work due to the subject's health	This is only calculated for parents/caregivers that were working, OR not working due to the child's health problems. If the parent is not working due to the child's health problems this is set to 100%. In all other cases total number of days missed from work because of the child's health problems, divided by the end date - start date +1 of the reported Month x100% and rounded to the nearest integer. The answer to Questionnaire section E question 1.
Parent's/caregiver's productivity at work limited by the subject's health per Month	This is only calculated for parents/caregivers that were working. The extent to which the parent's/caregiver's productivity while at work was limited by the subject's health per Month. The answer to Questionnaire section E question 1b.
Subject's health problems limited the parent's/caregiver's ability to engage in normal daily activities per Month	The extent to which the subject's health problems limited the parent's/caregiver's ability to engage in normal daily activities per Month. The answer to Questionnaire section E question 2.
How much the child's health has affected the child's usual activities per Month	The extent to which the child's health affected the child's usual activities per Month. The answer to Questionnaire section E question 3.
Impact of the subject's health problems on the parent's/caregiver's health per Month	The extent to which the subject's health problems impacted the parent's/caregiver's health per Month. The answer to Questionnaire section E question 4.
Inability of the parent/caregiver to care for other family members due to the subject's health per Month	The inability of the parent/caregiver to care for other family members due to the subject's health per Month. The answer to Questionnaire section E question 5. The result will be either "Yes" or "No".
Subject's health limited the parent's/caregiver's time spent with other family members each Month	The extent to which the subject's health limited the parent's/caregiver's time spent with other family members each Month.

	The answer to Questionnaire section E question 6. The result will be categorical as listed in the Questionnaire.
Percentage of days other family members missed from work due to the subject's health problems per Month	The percentage of days each Month that other family members missed from work due to the subject's health problems. Derived base on the Questionnaire section E question 7. Calculated as the number of days as recorded in question 7 divided by the number of days since the last study visit/telephone call. For subjects currently not in paid employment, the value will be 100% for parents/caregivers who were not employed due to the child's health problem and missing if this was not due the child's health problem.
Clinical diagnosis of eczema within the first 2 years after the RSV infection	Clinical diagnosis of eczema within the first 2 years after the RSV infection, as diagnosed by a physician and reported by the parent/caregiver. The result will be either "Yes" or "No". Derived based on the answer to Questionnaire section C until the Month 24 analysis visit.
Clinical diagnosis of allergic rhinitis within the first 2 years after the RSV infection	Clinical diagnosis of allergic rhinitis within the first 2 years after the RSV infection, as diagnosed by a physician and reported by the parent/caregiver. The result will be either "Yes" or "No". Derived based on the answer to Questionnaire section D until the Month 24 analysis visit.

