### ***Exploratory Endpoints***

The exploratory endpoints during the follow-up period are:

- The long-term impact of RSV and its treatment with lumicitabine or placebo on how the subject's health affects the normal daily activities of the subject, the parent/caregiver, and other family members as determined by:
  - The extent to which the subject's daily activities each month were limited by the subject's health.
  - The percentage of days each month that the parent/caregiver missed from work due to the subject's health.
  - The extent to which the parent's/caregiver's productivity while at work was limited by the subject's health.
  - The extent to which the subject's health problems limited the parent's/caregiver's ability to engage in normal daily activities.
  - The extent to which the subject's health problems impacted the parent's/caregiver's health.
  - The inability of the parent/caregiver to care for other family members due to the subject's health.
  - The extent to which the subject's health limited the parent's/caregiver's time spent with other family members.
  - The percentage of days each month that other family members missed from work due to the subject's health problems.
- Frequency of wheezing and clinical diagnosis of asthma by type of wheezing/asthma phenotype.

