### Section E: Questions of the Impact of the Child's Health on the Parent/Caregiver and Family

#### 1. Is the parent/caregiver currently in paid employment?

No 

a. Is the parent/caregiver currently not employed because of the child's health problems?

No

Yes

Yes 

a. Since the date of the last study site visit/telephone call, how many days did the parent/caregiver miss from work because of the child's health problems?

Total number of days missed from work because of the child's health problems:  
 \_\_\_\_\_ days

b. Since the date of the last study site visit/telephone call, how much did the child's health problems affect the ability of the parent/caregiver to be productive on the job (eg, complete tasks on time, get to work on time, pay attention when at work)? If your child's health, affected work only a little, instruct the parent/caregiver to choose a low number. Please circle a number below based on the response from parent/caregiver.

Child's health had  
no effect on  
parent's/caregiver's  
work productivity

0 1 2 3 4 5 6 7 8 9 10

Child's health  
completely prevented  
the parent/caregiver  
from being productive at  
work

2. Since the date of the last study site visit/telephone call, how much has the child's health problems affected the parent's/caregiver's availability to perform normal daily activities (other than work for pay)? By normal daily activities we mean the usual activities you perform, such as working around the house, gardening, shopping, childcare, exercising, studying, etc. If the child's health problem affected activities only a little, instruct the parent/caregiver to choose a low number. Please circle a number below based on the response from parent/caregiver.

Child's health had  
no effect on  
parent's/caregiver's  
normal daily  
activities

0 1 2 3 4 5 6 7 8 9 10

Child's health  
completely prevented  
parent/caregiver from  
doing normal daily  
activities

- 3. Since the date of the last study site visit/telephone call, how much has the child's health affected the child's usual activities? If the child's health had little effect on the child's usual activities, instruct the patient/caregiver to choose a low number. Please circle a number below based on the response from parent/caregiver.**

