Child's health had no effect on the child's usual activities	
 
 0	1	2	3	4	5	6	7	8	9	10	
 
	0	1	2	3	4	5	6	7	8	9	10	Child's health severely limited the child's usual activities
0	1	2	3	4	5	6	7	8	9	10			

- 4. Since the date of the last study site visit/telephone call, how much has the child's health affected the parent's/caregiver's health? If the child's health problem had little effect on the parent's/caregiver's health, instruct the patient/caregiver to choose a low number. Please circle a number below based on the response from parent/caregiver.**

Child's health had no effect on the parent's/caregiver's health	
 
 0	1	2	3	4	5	6	7	8	9	10	
 
	0	1	2	3	4	5	6	7	8	9	10	Child's health caused severe health problems for the parent/caregiver
0	1	2	3	4	5	6	7	8	9	10			

- 5. Since the date of the last study site visit/telephone call, has the child's health made it difficult for the caregiver to care for other family members?**

- No  
 Yes

- 6. Since the date of the last study site visit/telephone call, how often did the child's health limit the amount of time the parent/caregiver spent with other family members?**

- Rarely or never limited time  
 Occasionally limited time  
 Often limited time  
 Most of the time or always limited time

- 7. Since the date of the last study site visit/telephone call, how many days did other family members miss from work because of the child's health problems (eg, to stay home to care for the child or other family members, to take time off to take the child for medical visits, etc.)?**

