Total number of days that family members missed from work because of the child's health problems: \_\_\_\_ days

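### SAP Table 3 reports a parental-employment answer under the name of the child's activity limitation, and lets the interviewed parent's employment overwrite other family members' missed work

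*SAP*

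**What the plan says.** **Protocol.** Section 2.1.2 and the Synopsis list eight exploratory endpoints on the burden of the child's health. The first is the extent to which the child's "daily activities each month were limited by the" child's health. The last is the percentage of days each month that other family members missed from work.

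**Questionnaire (Protocol Attachment 2, Section E).**
- Question 1 asks whether the parent/caregiver is in paid employment. After a No, sub-item 1a asks: "Is the parent/caregiver currently not employed because of the" child's health problems.
- Question 3 asks how much the child's health affected the child's usual activities, on a scale from 0 to 10.
- Question 7 asks "how many days did other family members miss from work because of the" child's health problems. Its answer field reads "Total number of days that family members missed from work because of the" child's health problems.

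**SAP section 5.3.1, Table 3.**
- Row 1 is named for the child's daily activities as limited by the child's health. Its calculation begins "The parent/caregiver reports that they are not working due to" the child's health problems, cites Section E question 1, and gives Yes or No.
- Row 2 is the parent's own missed workdays. If the parent is not working because of the child's "health problems this is set to 100" percent.
- Row 5 is the child's usual activities: "The answer to Questionnaire section E question 3".
- The row on other family members divides question 7 days by the days since the last contact. It then adds a rule for parents out of work on account of the child: "For subjects currently not in paid employment, the value will be 100% for parents/caregivers who were not employed due to". Where a parent is out of work on other grounds, that rule leaves the value missing.

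**The concern.** Two rows do not measure what their names say.

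In row 1, a reader looking for the protocol's endpoint on the child would find a tabulation of parental non-employment. The protocol asks for an extent, and the row gives a Yes/No answer about a different person.

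In the other-family row, the employment status of the interviewed parent overrides an answer about other people. Question 7 stands outside the branches of question 1 and carries no employment condition, so it is asked whether or not the parent works. The questionnaire records no employment status for other family members. The children themselves were at most 36 months old at entry to the parent study, so the reference to subjects in paid employment can only mean the interviewed parent.

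Together, a single Yes to question 1a would produce Yes for the child's limitation, 100% for the parent's missed work, and 100% for other family members' missed work. The protocol keeps these as three separate endpoints.

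**Working it through.** The plan gives no figure to reproduce here. The check sets each row beside its source item and then applies the other-family rule as written.

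**1. Row against item**

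| SAP Table 3 row | Item used | What the item measures | Match |
|---|---|---|---|
| Row 1, child's daily activities | Question 1/1a, Yes/No | Parent's employment | No |
| Row 2, parent's missed days | Question 1, with 100% rule | Parent's own work | Same person |
| Row 5, child's usual activities | Question 3, 0 to 10 | Child's limitation | Yes |
| Other family members' missed days | Question 7, overridden by parent's employment | Other people's work | Only if the parent is employed |

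Leaving out eczema and allergic rhinitis, Table 3 has 9 burden rows against 8 burden endpoints in the protocol. The surplus arises because row 1 and row 5 both stand for the first endpoint, and only row 5 measures it.

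**2. The other-family rule applied**

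The documents give neither question 7 answers nor parental employment, so the inputs below are assumed, with a 30-day interval. The value from question 7 alone is 100 × days / 30, rounded to an integer.

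| Interviewed parent | Question 7 days | Question 7 alone | SAP rule |
|---|---|---|---|
| Not employed, because of the child | 0 | 0% | 100% |
| Not employed, because of the child | 5 | 5/30 = 16.7%, so 17% | 100% |
| Not employed, other reason | 5 | 17% | missing |
| Employed | 5 | 17% | 17% |

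When the parent is out of work because of the child, the two values in these examples differ by 83 or 100 percentage points. When the parent is out of work for another reason, a usable 17% is dropped.

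**3. Effect on a monthly mean**

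SAP section 2.4 gives 7 subjects; the split by treatment is not stated. If every question 7 answer in a group of n is 0 and one child's value is set to 100%, the group mean becomes 100/n:

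| n | 6 | 5 | 4 | 3 | 2 | 1 |
|---|---|---|---|---|---|---|
| Mean | 16.7% | 20% | 25% | 33.3% | 50% | 100% |

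Over all 7 children together it would be 100/7 = 14.3%. That is a scale reference only, because SAP sections 5.3.1 and 5.3.2 plan these summaries by treatment group.

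**The case against.** The strongest reply is about weight. Nothing is lost on the child's limitation: question 3 has its own row, is summarised by group and month, and also appears in the by-subject display, which has a column for each interview question. Row 1 states openly that it uses the parent's employment question. An extra row is not a fault in itself, since Table 3 also adds eczema and allergic rhinitis. All of this stands, and it makes row 1 a matter of a wrong name on a derivation.

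The effect of the other-family rule is also conditional. If all interviewed parents are employed, it changes nothing. The plan does not say explicitly that a mean of this percentage will be shown: SAP section 5.3.1 promises summary statistics without naming them, and Protocol section 11.4 speaks of frequency tabulations and listings. The means above therefore show what the rule can do, not what it will do.

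Two further cautions are fair. That row 1 gives No for an employed parent is the natural reading, but the SAP does not spell out that coding. And row 2 is not vouched for in full here. It divides missed workdays by calendar days, so a parent on an assumed five-day week who misses every workday scores 5/7 = 71%, against 100% for a parent out of work because of the child. The 100% rule at least concerns the right person in that row.

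None of this makes either definition correct. No other part of the SAP or protocol corrects them, and the SAP specified these summaries when it was already known that only 7 children had enrolled.

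**Conclusion.** Both mismatches hold on the text. Row 1 carries the protocol's endpoint name but reports parental non-employment, so on the natural reading the child of an employed parent counts as No even with 10 out of 10 on question 3. The other-family row replaces a valid question 7 answer with 100% or missing whenever the interviewed parent is not employed.

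The severity is minor. The endpoints are exploratory and descriptive, no hypothesis is tested, and no primary, secondary or safety output is touched. The question 7 row is right for employed parents, and the raw answers allow a reader to see the discrepancy. How often the override would apply cannot be judged from the documents. The two mismatches themselves rest on no assumption; only the sizes shown do.

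**What to change.** In SAP Table 3:
- **Row 1:** rename it as parent/caregiver not employed because of the child's health (question 1a), or delete it.
- **Row 5:** name the question 3 row as the protocol's endpoint on the child's daily activities.
- **Other family members' missed work:** delete the sentence on paid employment and derive the percentage from question 7 for every respondent. Optionally, add a note that question 7 is a total over family members, so the value can exceed 100%. For example, two relatives each missing 20 of an assumed 30 days give 40/30 = 133%.

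The cost is the definitions and labels in these rows and the matching programs. The questionnaire and the data already collected are sufficient.
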